8.1.2 Routine data

CDSA individual consultation data

As part of the CDSA intervention, healthcare providers will be asked to use MedAL-R during their consultations. When they do so, they will routinely enter all data necessary for the clinical management of children 0 – 59 months of age into MedAL-R. Data used within TIMCI will cover clinical presentation (including symptoms and dangers signs), medical history (including HIV and TB status if known), all physical exams and measurements relevant for clinical assessment (including pulse oximetry), and laboratory investigations. Automated recommendations from CDSA on diagnosis and child management will also be collected, as well as healthcare provider's agreement or disagreement with these recommendations and possible additional diagnoses and treatments, which will be manually entered. A description of the variables extracted from CDSA is available with other individual data in the appendix.

HMIS aggregate facility data

HMIS data will include the total number of outpatient consultations – for all patients and for children 0 – 59 months of age (disaggregated by new and follow-up visit if possible) –, disease

burden, and any other relevant indicators if available (such as referral rate or mortality rate), disaggregated by age and sex if routinely collected with this granularity.

8.1.3 Other mixed methods studies

Some data required for the SPA (observation and caregiver exit interview) are common with the pragmatic cluster RCT data and will not be collected again. To reconstruct the full SPA dataset, SPA observation and caregiver exit interviews will be linked with the pragmatic cluster RCT as described in Section 10.4.3. The consultation observation will be conducted by a standardised clinical observer who will record information asked or provided by the healthcare provider and / or caregiver during the consultation on key aspects relating to adherence to IMCI (or national guidelines) and the use of pulse oximetry and CDSA (in applicable arms). The observer will not ask any questions directly of the caregiver, but at the end of the consultation will ask a limited number of questions of the healthcare provider to record diagnosis and management.

In line with the WHO guidance on Ethical Issues in Patient Safety Research, observers in Tanzania (deemed to have sufficient experience and expertise) will be advised to intervene in the consultation only in the event that they witness an error, or suspect an imminent error, during the consultation that is "highly likely to result in direct, severe or irreversible harm" and could be mitigated by their intervention. Should they intervene, the observer will record the intervention in the sick child observation protocol instrument. No information on individual performance will be shared with supervisors, or anyone else. However, in order to mitigate the ethical issues of non-intervention when poor performance has been observed, observers in Tanzania will provide a short supportive feedback to the individual providers if they agree to it at the end of the period of observation. This will be structured in line with supervision procedures of respective MOHs. Feedback provided will be recorded.

In India, observers will not intervene or provide feedback as they are deemed not to have sufficient experience or expertise.

The exit interview will be performed after the consultation by a non-clinical research assistant who will record responses to questions on additional sociodemographic and clinical details and experience of care. The healthcare provider interviews will collect information from healthcare providers involved in the care of children 0 – 59 months, on qualifications, in-service training and experience related to child health and pulse oximetry and experience of the working environment. The facility assessment will focus on the basic infrastructure, staffing, services, diagnostics and medicines relevant to child health, with additional information collected on pulse oximetry, records and reporting and management. At the end of the SPA assessment at the facility, the clinical observer and research assistant will note down additional (prompted) summary observations about the use of pulse oximeter and / or CDSA in the facility.

For the process mapping and time-flow study, pre-drawn, country-specific process maps will be reviewed and modified by research assistants with informal input from facility staff and

observation. Time data will be recorded using an individual follow-through (timing one child from arrival to exit) and/or area-based (waiting area timing, consultation timing, further diagnostic timing, etc.) approach. Notes based on non-participant observation will be taken by research assistants on observations within the facility (e.g. if devices are not charged, waiting rooms are crowded, the type of interactions between patients and providers, change in provision of care (e.g. new triage system introduced)) and will not include any individual patient data.

If FGDs are conducted, they will be facilitated by a moderator and have an assigned note taker (in charge of documentation). Prior to moving to the main topics of discussion, ice-breaker exercises will be used to establish trust with participants and to provide an overview of the topic for discussion (pulse oximetry with or without CDSA). The FGDs with healthcare providers (and possibly caregivers) will use clinical vignettes which will be presented and jointly discussed.

Qualitative data from IDIs, and KIIs will be collected by trained qualitative research assistants using a voice recorder, , in addition to paper-based notes and drawings. Interviews will be conducted using a semi-structured guideline interview tool, with emphasis placed on building trust and using open-ended questions with probes.

Key-informant interviews with stakeholders will either be conducted in-person or via telephone/Skype/Zoom. Interviews will be scheduled and interview questions shared in advance if wished. Surveys (using an online survey tool such as Survey Monkey) for selected stakeholders will be sent out on a regular basis (quarterly) via email. Participants will be asked to answer the questions and upload additional documents. A single reminder will be sent in case no response was received. Documents will be requested from partners on a quarterly basis; a desk-review will be conducted and data entered into a document matrix.

8.1.4 Cost and cost-effectiveness study

Cost data collection will occur in all arms as shown in Fig. 3.

Definition of costs using an activity-based approach

An activity-based approach will be explored using available cost data. Specific activities in the intervention will be allocated to different cost centres. In order to provide cost estimates that will be as managerially-, policy- and programmatically-relevant as possible, the cost analysis will adopt this approach as this separate research costs from the main programme implementation costs. The focus will be on those costs that are expected to change with the introduction of pulse oximetry and CDSAs. Costs including utilities and large equipment costs will remain the same with or without the introduction of pulse oximetry and CDSAs.

To apply the activity-based approach, we will identify specific activities that are to be costed. These will be referred to as "cost centres" (See **Tab. 6**). Cost centres are a way in which the

resources used to produce the intervention activities—and the costs of those resources—are grouped. Cost centres are defined in such a way that:

- The sum of the cost centres is comprehensive—including all the resources used to produce each and every activity of the program—and together, the entire program, and
- They are mutually exclusive—thus avoiding double counting any of the resources used to provide the program.

It is important to note that this cost methodology is not comprehensive. As described in 5.8, it does not include the indirect costs incurred by the consumer (patient) e.g. the caregiver's time or transport costs. Rather, it focuses exclusively on the provider's direct costs, whether borne by the health system or paid out of pocket by the patient's household. The cost resources for each cost centre may differ between Tanzania and India according to availability of services.

Tab. 6. Activity-Based Cost Centres of the TIMCI programme.

1	Training cost for staff involved in delivering the programme:
	
- Consumable costs (including where applicable stationery, and other consumables) - Personnel costs- Overhead costs (including where applicable, rent for training venue, administrative costs, per diems and transport costs, and other overheads)
2	Delivery of intervention
	
- Annualized¹ fixed/equipment costs (including pulse oximetry device and CDSA tablet costs)- Consumable costs (including medicines, diagnostic tests, and other consumables) - Personnel costs
5	Out of pocket costs
	
- Any out of pocket costs paid by patients' households to the health system to access care and prescribed treatment will be collected, including resources purchased outside the facility due to unavailability in the facility. However, care not prescribed by facility healthcare professionals will not be included.

1. Since costing needs to account for both capital and recurrent costs, annualizing capital costs (i.e. calculating the annual value of a capital item) is the easiest way of combining capital and recurrent costs meaningfully. Annualizing capital cost is based on three pieces of important information: the initial purchase price of the item, its expected useful life, and a discount rate

Sources of cost data

Personnel and procurement units of the organisations involved in the TIMCI intervention especially through different local PATH offices and sampled facilities will be sourced for the cost data. Centrally available databases will be used to estimate personnel and consumable (including medicines and diagnostics) costs where available.

Start-up costs which will include training and community sensitisation costs will be collected pre facility enrolment and intervention. After facility enrolment, cost data will be collected from non-medical administrative personnel. All personnel costs for those involved in each arm of the intervention will also be collected since time in supervision, time of administrative support staff is as important as that of front-line staff seeing patients. Personnel time, and volumes of

diagnostic tests and treatments prescribed, will be obtained from the time-flow and service provision assessment studies. Data on time required for supervision and administrative tasks such as taking patient notes will be obtained from the senior medical professional at the facility, along with information on grades of personnel. Salaries of personnel according to grade will be sourced from centrally available databases which would include government salary publications for health facility workers (medical and non-medical) and complemented with salary costs sourced from health facility administrative databases where needed. Costs of consumables will also be sourced centrally where available and would for instance include cost of items on the National Essential Medicine List. Referral and hospitalization costs will be sourced from interviewing senior administrative personnel at referral health facilities.

Total programme cost and cost per child will be estimated. We will collect administrative data from appropriate levels in each country depending on organization of the specific health system, and will use time-flow data collected elsewhere in the project before and after the intervention.

The table below lists the broad areas of cost data collection for each cost centre and the respective data sources.

Tab. 7. Sources of cost data

Type of Cost		Identification	Measurement		Valuation	
		Categories	Costing method	Sources of data	Valuation methods	Sources of data
Recurrent	Personnel (staff)	All staff involved (field workers and managers, administrators, support staff (drivers), etc)	Percentage of time spent on different activities within TIMCI; grade of personnel	Time data collected by operational research	Gross remuneration package costs	Centrally from government databases and complemented with provider's payroll department
	Consumables	Disposable items used per child per intervention	Quantity of consumables used per child	Medical personnel at health facility	Market prices	Centrally from government databases and complemented with provider's procurement department
	Equipment/ Capital (incurred every few years)	Pulse oximetry devices, tablets etc	Annualised cost of items	Interview, observations, and timing	Replacement prices	Provider's financial syndicate office
	Out of pocket costs	All out of pocket costs paid by patients' households to the health system for fever management	Direct fees and charges paid by households to health systems	Cost borne by households	Financial cost	Cost data collected from health system administrative records; information from interview of senior non-medical personnel

Definitions of types of costs and data to be collected

Staff time: For each activity within TIMCI, the responsible staff member involved with the activity will be identified. Secondly the time involved will be ascertained from the time-flow study and quantified. Supervision costs will similarly be estimated.

Consumables: The type and quantity of medicines, diagnostic tests and consumables used for each intervention arm will be identified. In addition, unit costs of each consumable item will be obtained (for example the cost of a box of cotton wool balls) and the size of unit (the number of cotton wool balls in each box).

Equipment: All equipment used for each activity will be identified and the price for which it was purchased. For the equipment costing, the lifespan for the equipment (usually between 3 – 5 years for smaller items including electronic tablets and pulse oximetry devices) will be obtained and annualized. Annualization will follow the cost recovery methodology where item cost, life span, and a defined interest rate is used to estimate the annual cost of an item. For equipment that is shared with other programmes, the time spent per consultation will be obtained as a percentage of total time spent using each equipment and used to calculate the cost associated with the intervention after annualization. For donated equipment, market price information will be sought.

Equipment inventories and training records will be used to collect retrospective costs. Time spent by staff on consultations with children 0 – 59 months of age will be collected from data obtained in the time-flow study. Time costs will then be determined by combining staff annual salaries obtained from government sources and/or payroll offices with time spent per intervention. Where applicable, this personnel cost will be disclosed only to the principal researcher without the identity of staff involved. Consumables used will be examined to determine the unit cost of each consumable, while equipment will be annualized to determine their unit costs.

All capital and start-up costs will be annualised using an appropriate length of life and discount rate. Out of pocket payments to health systems borne by households will be estimated to capture all health system costs. These costs might vary across different settings since there might be flat rates in one setting and a varied fee schedule in another. Hence, the cost data collection for out of pocket payments will be country specific. The cost of hospital referrals where applicable, will also be estimated from interviews with senior healthcare professionals at the hospital level.

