5.8 Cost and cost-effectiveness study

The economic evaluation will involve a cost and cost-effectiveness analysis using direct health system costs in which financial and economic costs will be assessed. The scope of the costing will cover only intervention costs and not research-based costs, and will include costs incurred by the health system as well as estimated direct costs paid out of pocket by the households to the health system. It is important to note that this cost methodology is not comprehensive. It does not include the indirect costs incurred by the consumer (patient) e.g. the caregiver's time

or transport costs. Rather, it focuses exclusively on the provider's direct costs, whether borne by the health system or paid out of pocket by the patient's household.

The approach that has been taken in applying this methodology has been to capture what is thought to be the "most likely" cost scenario, on average. In identifying this "most likely" cost scenario, effort will be made to supplement the analysis with a discussion about factors that influence the level of costs (e.g. the number of trainees per training, or the frequency of supervision) so as to provide a type of sensitivity analysis of the robustness of the estimates. Cost scenarios will also guide possible future programme scale up. The cost resources for each cost centre might differ between India and Tanzania. For instance, at some facilities laboratory tests or some treatments may not be available, and patients have to be referred elsewhere: we will have to take account of these differences.

Research-based costs are excluded to enable the costing to provide guidance on future replication and potential scale up of the intervention. Full and incremental costing involving an activity-based and ingredient-based approach will be used. When available, effectiveness data will be combined with the cost data and cost per DALY averted will be estimated as outlined in 8.3.3. The costing and cost-effectiveness will use a 12-month time frame and a 3% discount rate. Where applicable, discount rates will be adjusted to prevailing rates at country-level.

6 Participants, interventions, and outcomes

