6.4.4 Cost and cost-effectiveness study

- Full implementation cost of the intervention per focal country (cost to health system as well as direct costs paid by the household to the health system)
- Cost per child screened using pulse oximetry devices and CDSA where applicable, compared to cost per child in routine care.
- Cost per DALY averted attributed to the introduction of pulse oximetry both with and without CDSAs modelled on proportions referred to hospital on day zero or by day 7 or requiring secondary hospitalization by day 28 in each arm and the predicted outcomes in each case, using published literature supplemented where necessary by expert opinion. We will utilize data on any other severe outcomes and also use predictors of severity on children who are admitted to hospital.

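### Protocol Tab. 7 limits household out-of-pocket cost to fever management, although the trial and the rest of the costing plan cover any illness

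*Protocol*

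**What the plan says.** Household payments enter the costing in five places in the protocol.

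- Section 5.8 includes "as well as estimated direct costs paid out of pocket by the households to the health system". It adds, on the costing as a whole, that "it focuses exclusively on the provider's direct costs", whether the health system or the household bears them.
- Section 6.4.4 makes them part of the first cost outcome: "cost to health system as well as direct costs paid by the household to the health system".
- Section 8.1.4, Tab. 6, cost centre 5, covers household payments for access to care and for prescribed treatment, "including resources purchased outside the facility due to unavailability in the facility". Care that facility staff did not prescribe is left out.
- Section 8.1.4, Tab. 7, defines the category as everything paid out of pocket by patients' "households to the health system for fever management". The costing method is fees and charges paid to health systems.
- The text after Tab. 7 says: "Out of pocket payments to health systems borne by households will be estimated to capture all health system costs".

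Section 8.3.3 obtains unit cost by dividing total cost by the sample size, and combines the cost data with effectiveness data to give cost per DALY averted. The SAP defines no cost outcome, so it does not settle the matter.

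**The concern.** Tab. 7 is where Section 8.1.4 sets out, for each cost centre, what is collected and from where. A costing team working from it would collect fever-related household payments in a trial where fever is only one reason for attending. The resulting cost per child would not describe the population in which effectiveness is measured.

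A second, smaller mismatch concerns prescribed items that the family buys elsewhere because the facility has none. Tab. 6 counts them. Section 5.8 and Tab. 7 are worded as payments to the health system. The plan does not say which source would measure such purchases.

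**Working it through.** The protocol gives no out-of-pocket amount, fever share or DALY figure, so there is no figure to reproduce. The check compares the passages and then uses simple algebra.

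**1. Scope, side by side**

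| Place in protocol | Limit by illness | Purchases outside the facility |
|---|---|---|
| 5.8 | none | not mentioned; provider's direct costs |
| 6.4.4 | none | not mentioned |
| 8.1.4, Tab. 6 | none | included if prescribed |
| 8.1.4, Tab. 7 | fever management | not mentioned; fees and charges to health systems |
| 8.1.4, text after Tab. 7 | none | not mentioned |

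On illness, Tab. 7 stands alone against the other four.

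**2. Population.** Section 6.2.1 admits children consulting for any illness and excludes trauma-only visits. Section 6.4.2 lists fever beside cough or difficulty breathing, diarrhoea and other complaints. Fever is not named as a criterion for oximetry in Section 6.3. The criteria agreed for Tanzania are age under 2 months, cough or difficulty breathing, or an IMCI yellow or red classification. In India oximetry is for all sick children under five.

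**3. Cost per child.** Let c be the mean household payment to the health system per enrolled child, f the share of it that is for fever management, and N the number of children. Take the sample size in Section 8.3.3 to mean all enrolled children.

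- All illnesses: N × c / N = c.
- Tab. 7 as written: N × f × c / N = f × c.
- Shortfall: (1 − f) × c, a fraction (1 − f) of the household component.

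With f assumed between 0.3 and 0.8, the shortfall runs from 1 − 0.8 = 20% to 1 − 0.3 = 70% of the household component. As a share of total cost per child it is (1 − f) × c / (H + c), where H is the cost borne by the health system. That is smaller whenever H is above zero, and it cannot be evaluated without c and H.

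**4. Cost per DALY averted.** Let D be DALYs averted per child and Δ the difference between arms in means per child. Dropping non-fever payments changes the ratio by Δ[(1 − f) × c] / D. This is zero when mean non-fever payments are equal in the arms. Section 4 names referral decisions and antimicrobial prescription as targets of the intervention, so a difference is plausible, but the documents give no data on it.

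**5. Outside purchases.** Let o be mean spending per child on prescribed items bought elsewhere. Tab. 6 then gives c + o, and the payments-to-the-health-system wording gives c. For measurement, Tab. 7 lists cost borne by households as its source and names no instrument. For valuation it lists administrative records and an interview with senior non-medical staff. Form TIMCI-04a (Section 6.5.1, Tab. 4) records visit costs reported by the caregiver, but nothing says that it covers outside purchases or feeds the costing. Whether o is measured is therefore open.

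**The case against.** The best reply is that the plan has one loosely worded definition and one stray phrase. Four of the five places carry no illness limit, and the sentence after Tab. 7 aims at all health system costs. Tab. 6 puts payments to the health system and outside purchases in a single sentence, so the second can be read as spelling out the first. Section 8.1.4 introduces Tab. 7 as listing broad areas and says that out-of-pocket collection will be country specific. The costing questionnaires listed in Section 12.2 are not in the text available here, so what will be asked is unknown.

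Most of this stands. A reader might infer three competing definitions; the documents do not support that, because everything except the fever phrase can be read together. A reader might also infer that the named sources are unable to register outside purchases. That goes too far, given the household entry in the measurement column and the costs reported by caregivers.

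The reply does not remove the fever limit. It stands in the data-collection table, and leftover wording still restricts scope if followed.

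**Conclusion.** Tab. 7 contradicts the rest of the costing plan and the trial population on illness scope. Followed as written, it understates household cost per child by the non-fever share of payments. That share is unknown; the 20% to 70% above rests wholly on an assumed f. The cough or difficulty breathing figure of 40–70% of attendees in Section 6.3 cannot stand in for it, because a child may have both cough and fever. Where facilities charge households little, the absolute error is small.

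A reader might infer that cost per DALY averted is necessarily wrong. It is not: it moves only if non-fever payments differ between arms, which the documents leave open.

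The treatment of outside purchases is unclear rather than contradictory, and needs a sentence and a source. All of this concerns the economic sub-study. The primary outcomes, sample size and error rates are untouched.

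**What to change.** 1. Delete the closing three words of the out-of-pocket category in Tab. 7, so that it covers every enrolled illness. This costs nothing beyond the wording change.

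2. Align Tab. 6 with Section 5.8, Tab. 7 and the paragraph in Section 8.1.4 that repeats the limit to the provider's direct costs. There are two ways to do so.

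   - Keep outside purchases and name a source already in the study that can measure them. Candidates are costs reported by caregivers, or the exit interview and facility medicine-availability data of the service provision assessment (Section 8.1.3). An added question may be needed, and the assessment covers six facilities per arm. Prescription records alone will not do: Section 6.5.1 records what was prescribed, but the documents do not show what the facility supplied to each child. The plan must also say how these items are kept out of the consumables cost. Section 8.1.4 already takes treatment volumes from what was prescribed and requires cost centres that do not overlap.
   - Otherwise, state that outside purchases are not captured and report this as a limitation. This needs no new data, but leaves the household component narrower than Tab. 6 now promises.
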